V591-001-02	14-SEP-2020	The protocol amendment 01 is being amended to expand age range for Part 2B (reduce lower limit to >55 years old). Additionally, clarifications to the inclusion/exclusion criteria and the criteria that will trigger a study pause, as well corrections of typographical errors, are included in the amendment.
V591-001-01	13-AUG-2020	The original protocol is being amended to revise several exclusion criteria, add a second vaccination of 10^5 TCID ₅₀ on Day 169 for participant receiving the lowest first dose of 10^4 TCID ₅₀ Panel (the new Panel F) and specify sentinel dosing arrangements in Panels A, B and Panel E (the highest single dose panel).
Original Protocol (V591-001-00)	17-JUL-2020	Not applicable

PROTOCOL AMENDMENT SUMMARY OF CHANGES

Amendment: [04]

Overall Rationale for the Amendments:

An evaluation of available Day 29 immunogenicity data, including both ELISA and a pseudo-neutralization assay, indicated that the immune responses elicited by V591 were inferior to those following natural infection and to those reported for other SARS-CoV-2/COVID-19 vaccines. Thus, V591 was not predicted to protect against disease caused by SARS-CoV-2. Based on these data, the Sponsor has decided to terminate the V591-001 study, thereby allowing participants to seek COVID-19 vaccinations outside of the study. V591 was generally well-tolerated, and the decision to discontinue this trial was based solely on the immunogenicity data. This amendment is intended to document the termination of the study as permitted under flexible protocol language. Participants will complete activities through at least Day 56, which includes all protocol specified safety laboratory and routine AE assessments. Participants will not be actively followed beyond end of trial activities (to occur on or after Day 56); spontaneous reporting of SAEs and other protocol-specified events may continue through the protocol specified durations. In place of an Interim Analysis of data, the final study analysis will be performed on the collected dataset through at least Day 56.

Summary of Changes Table:

Section # and Name	Description of Change	Brief Rationale
1.1 Synopsis 1.3, Schedule of Activities 3, Hypotheses, Objectives, and Endpoints 4.1, Overall Design 4.2.1.2 Immunogenicity Endpoints 8.2.1, Serum Neutralizing Antibodies Measured by PNA	Changed “plaque reduction neutralization test (PRNT)” to “Pseudo-virus Neutralization Assay (PNA)” throughout the protocol. Added PNA in Abbreviation List	Pseudo-virus Neutralization Assay (PNA) will be used to measure serum neutralization antibodies against SARS-CoV-2 spike protein. Both PNA and PRNT test for the same neutralization antibodies and report an NT50 titer. There is no impact on data report for the assay change.

Section # and Name	Description of Change	Brief Rationale
8.11.5, Critical Procedures Based on Study Objectives: Timing of Procedure 9, Statistical Analysis Plan 10.8, Appendix 8: Blood Volume Table Appendix 10: Abbreviations		
6.7.1, Stopping Rules 8.3.5 Vaccine Report Card	Removed “severe” from “Severe (Grade 3 or higher) at the beginning of bullets 4 and 5. Removed “(severe)” after grade 3 in the last sentence in the 2 nd paragraph.	Toxicity grade is used for the stopping rule assessment. In some case intensity may not match toxicity grade.
8.11.4, Poststudy	Added text to clarify required procedures at the final post-study visit at least 56 days post the last vaccination.	The sponsor has decided to terminate the study based on the immunogenicity results. This clarification is provisioned by the language as indicated in Section 8.11.6 Study Design/Dosing/Procedures Modifications Permitted Within Protocol Parameters: “Modification of the immunogenicity sampling schedule, including omitting Timepoints”

Section # and Name	Description of Change	Brief Rationale
10.2, Appendix 2: Clinical Laboratory Tests	Changed “HbA1c” to “HbA1c (required at screening only)” in the table “Protocol-required Safety Laboratory Assessments”.	HbA1c measurement is required at screening visit only in order to fulfill exclusion criteria #26. The inclusion of HbA1C in Appendix 2, Table 14 is not intended to indicate that it is a Protocol-required Safety Laboratory Assessment that must be regularly assessed along with hematology and chemistry assessments.

Table of Contents

DOCUMENT HISTORY	3
PROTOCOL AMENDMENT SUMMARY OF CHANGES.....	4
1 PROTOCOL SUMMARY	15
1.1 Synopsis.....	15
1.2 Schema	19
1.3 Schedule of Activities.....	20
1.3.1 SoA for 1-Dose Panels.....	20
1.3.2 SoA for 2-Dose Panels (Day 1, Day 57).....	25
1.3.3 SoA for 2-Dose Panels (Day 1, Day 169).....	30

1 PROTOCOL SUMMARY

1.1 Synopsis

Protocol Title: A Phase 1/Phase 2, Randomized, Double-Blind, Placebo-Controlled, Dose-Ranging Trial to Evaluate the Safety, Tolerability and Immunogenicity of V591 (COVID-19 Vaccine) in Healthy Younger and Older Participants

Short Title: Phase 1/Phase 2 Dose Ranging Trial to Assess Safety, Tolerability, and Immunogenicity of V591 (COVID-19 Vaccine) in Healthy Participants

Acronym: NA

Hypotheses, Objectives, and Endpoints:

Healthy male participants and female participants between the ages of 18-55 years (inclusive) of age in Parts 1 and 2A (younger adults) and > 55 years of age in Part 2B (older adults)

Primary Objectives	Primary Endpoints
To assess the safety and tolerability of V591 compared with placebo	Solicited injection site adverse events from Day 1 through Day 5 after any study intervention Solicited systemic adverse events from Day 1 through Day 14 after any study intervention Unsolicited adverse events from Day 1 through Day 28 after any study intervention SAEs from Day 1 throughout the duration of study Medical attended AEs (MAAEs) collected from Day 1 throughout the duration of study
Secondary Objectives	Secondary Endpoints
To compare the humoral immunogenicity of V591 with placebo at Day 29 (all panels) and Day 85 (Panels A, B, I, and J) or Day 197 (Panels K and L)	Anti-SARS-CoV-2 spike serum neutralizing antibody (nAb) responses, as measured by Pseudo-virus Neutralization Assay (PNA) Anti-SARS-CoV-2 spike Immunoglobulin G (IgG) responses, as measured by ELISA
To evaluate the humoral immunogenicity of V591 at all timepoints with serum collection	Anti-SARS-CoV-2 spike serum nAb responses, as measured by Pseudo-virus Neutralization Assay (PNA) Anti-SARS-CoV-2 spike IgG responses, as measured by ELISA

Overall Design:

Study Phase	Phase 1/Phase 2
Primary Purpose	Prevention
Indication	COVID-19
Population	Healthy adult participants
Study Type	Interventional
Intervention Model	Sequential This is a multi-site study.
Type of Control	Placebo
Study Blinding	Double-blind
Blinding Roles	Participants or Subjects Investigator Outcomes Assessor
Estimated Duration of Study	The Sponsor estimates that the study will require approximately 30 months from the time the first participant (or their legally acceptable representative) provides documented informed consent until the last participant's last study-related contact.

Number of Participants:

Approximately 260 participants will be allocated/randomized.

Intervention Groups and Duration:

Intervention Groups	Intervention Group Name	Drug	Dose Strength	Dose Frequency	Route of Administration	Vaccination Regimen	Use
	Part 1 (18 to 55 years old) Sentinel Cohort						
	Panel A	V591	1·10 ⁵ TCID ₅₀	2 doses	IM	IM injection on Day 1 and Day 57	Experimental Treatment
	Panel B	V591	1·10 ⁶ TCID ₅₀				
	Panels A, B	Placebo	NA	2 doses	IM	IM injection on Day 1 and Day 57	Placebo
Part 2A (18 to 55 years old)							
	Panel C	V591	1·10 ⁵ TCID ₅₀	Single Dose	IM	Single IM injection on Day 1	Experimental Treatment
	Panel D	V591	1·10 ⁶ TCID ₅₀				
	Panel E	V591	1·10 ⁷ TCID ₅₀				
	Panels C-E	Placebo	NA	Single Dose	IM	Single IM injection on Day 1	Placebo
	Panels F	V591	1·10 ⁴ TCID ₅₀ / 1·10 ⁵ TCID ₅₀	2 doses	IM	IM injection on Day 1 and Day 169	Experimental Treatment
	Panel F	Placebo	NA	2 doses	IM	IM injection on Day 1 and Day 169	Placebo
Part 2B (> 55 years old)							
	Panel G	V591	1·10 ⁵ TCID ₅₀	Single Dose	IM	Single IM injection on Day 1	Experimental Treatment
	Panel H	V591	1·10 ⁶ TCID ₅₀				
	Panels G and H	Placebo	NA	Single Dose	IM	Single IM injection on Day 1	Placebo
	Panel I	V591	1·10 ⁵ TCID ₅₀	2 doses	IM	IM injection on Day 1 and Day 57	Experimental Treatment
	Panel J	V591	1·10 ⁶ TCID ₅₀				
	Panels I and J	Placebo	NA	2 doses	IM	IM injection on Day 1 and Day 57	Placebo
	Panel K	V591	1·10 ⁵ TCID ₅₀	2 doses	IM	IM injection on Day 1 and Day 169	Experimental Treatment
	Panel L	V591	1·10 ⁶ TCID ₅₀				
	Panels K and L	Placebo	NA	2 doses	IM	IM injection on Day 1 and Day 169	Placebo
Abbreviations: IM: intramuscular; NA=not applicable; TCID ₅₀ =Median tissue culture infectious dose							
	Other current or former name(s) or alias(es) for study intervention(s) are as follows: NA						
Total Number of Intervention Groups/ Arms	260 participants (10 in Part 1 younger sentinel cohort, 100 in Part 2A younger cohort and 150 in Part 2B older cohort) will participate in the study that will include a total of 4 dose-levels and 12 Panels. Under each panel, participants will be randomized to receive V591 or placebo in a 4:1 ratio.						

Duration of Participation	Each participant will participate in the study for approximately 15 to 19 months for 2-dose panels and 13 months for 1-dose panels from the time the participant provides documented informed consent through the final contact. After a screening phase of 28 days, each participant will be receiving either 2 doses of assigned intervention (Panels A, B, F, I, J, K and L) or 1 dose of assigned intervention (Panels C-E and G-H). After the last vaccination, each participant will be followed for 12 months.
---------------------------	-----------------------------------------------------------------------------------------------------------------------------------------------------------------------------------------------------------------------------------------------------------------------------------------------------------------------------------------------------------------------------------------------------------------------------------------------------------------------------------------------------------------------

Study Governance Committees:

Steering Committee	No
Executive Oversight Committee	No
Data Monitoring Committee	Yes
Clinical Adjudication Committee	No
Insert Other Oversight Committee	No
Study governance considerations are outlined in Appendix 1.	

Study Accepts Healthy Volunteers: Yes

A list of abbreviations used in this document can be found in Appendix 10.

1.2 Schema

The study design is depicted in [Table 1](#) and [Figure 1](#).

Table 1 V591/Placebo Dose Scheme

Part 1 (18 to 55 years old) Sentinel Cohort		Part 2A (18 to 55 years old)				Part 2B (> 55 years old)					
Sentinel/2-dose (Day 1, Day 57)		1-dose			2-dose (Day 1, Day 169)	1-dose		2-dose (Day 1, Day 57)		2-dose (Day 1, Day 169)	
Panel A (n=5)	Panel B (n=5)	Panel C (n=25)	Panel D (n=25)	Panel E (n=25)	Panel F (n=25)	Panel G (n=25)	Panel H (n=25)	Panel I (n=25)	Panel J (n=25)	Panel K (n=25)	Panel L (n=25)
10 ⁵ TCID ₅₀	10 ⁶ TCID ₅₀										
		10 ⁵ TCID ₅₀	10 ⁶ TCID ₅₀								
				10 ⁷ TCID ₅₀	10 ⁴ TCID ₅₀ / 10 ⁵ TCID ₅₀						
						10 ⁵ TCID ₅₀	10 ⁶ TCID ₅₀				
								10 ⁵ TCID ₅₀	10 ⁶ TCID ₅₀	10 ⁵ TCID ₅₀	10 ⁶ TCID ₅₀

FIH=first in human; n=number of participants; siDMC= Standing Internal Data Monitoring Committee; TCID₅₀=median tissue culture infectious dose

- Within each panel, participants will be randomized to receive V591 or Placebo in a 4:1 ratio according to a computer-generated allocation schedule. The suggested doses may be adjusted downward based on evaluation of safety or tolerability data observed in previous participants.
- Part 2A and Part 2B may initiate simultaneously based upon siDMC recommendation following review of at least seven days of safety data from n = 5 participants from each panel in Part 1 after their Day 1 vaccination. The second vaccination for Panel F and Panels I-L in Part 2B may initiate based upon siDMC recommendation following review of at least seven days of safety data from n = 5 participants from each panel in Part 1 after their Day 57 vaccination.
- If available, Part 2A and Part 2B may initiate simultaneously based upon siDMC recommendation following review of safety and tolerability data from the COVID-19-101 study (V591 FIH study sponsored by the Institut Pasteur).
- As safety precaution, the enrollment for Panel E, the highest dose panel, will begin Day 1 vaccination with at a minimum five sentinel participants.

1.3 Schedule of Activities

1.3.1 SoA for 1-Dose Panels

1-dose Panels C-E and G-H													
	Screening	Study Day										Post-Study	Notes
Scheduled Hour, Day, Week, etc.	Screening -28 to -1 ^b	Day 1 Pre-dose	1	2 ^a	8±1	15±1	29±3	57±3	85±3	115±7	211±14	365±14	Section 8.11.5 Details on variance in procedure collection times
Administrative Procedures													
Informed Consent	X												Section 8.1.1.1
Informed Consent for Future Biomedical Research	X												Section 8.1.1.2
Demographics	X												
Inclusion/Exclusion Criteria	X	X											Section 5.0
Participant ID Card	X												Section 8.1.3
Medical History & Vaccination History	X												Section 8.1.4
Prior/Concomitant Medication Review	X	X	X	X	X	X	X	X	X	X	X	X	Sections 6.6, 8.1.5 Including Non-study Vaccination Review
Assignment of Screening Numbers	X												Section 8.1.6
Assignment of Randomization Number		X											Sections 5.5 and 8.1.7
COVID-19 Symptoms Training		X				X	X	X	X	X	X		Section 8.3.7
V591/Placebo Administration			X										Section 8.1.8
Clinical Procedures/ Safety Assessment													
Full physical examination	X	X									X	X	Section 8.3.1.1
Symptoms driven physical exam			X		X	X	X	X	X	X			Section 8.3.1.2 Only to be conducted if participant symptoms warrant an exam or at investigator's discretion

1-dose Panels C-E and G-H														
	Screening	Study Day											Post-Study	Notes
Scheduled Hour, Day, Week, etc.	Screening -28 to -1 ^b	Day 1 Pre-dose	1	2 ^a	8±1	15±1	29±3	57±3	85±3	115±7	211±14	365±14		Section 8.11.5 Details on variance in procedure collection times
Targeted physical examination of injection site			X		X	X								Section 8.3.1.3 Panel E: At ~ 8 hours after vaccination on Day 1 for the five sentinel participants. All other panels: At ~1 hour postdose on Day 1.
Height	X													Section 8.3.1.4
Weight	X												X	Section 8.3.1.4
Semi-recumbent Vital Signs (Blood Pressure [BP] and Heart Rate [HR] and Respiratory Rate [RR])	X	X	X		X	X	X	X	X	X	X	X	X	Section 8.3.2 Day 1 predose measurements will be done within ~ 3 hours of dosing. Day 1 postdose measurements: Panel E: At ~ 8 hours after vaccination on Day 1 for the five sentinel participants. All other Panels: will be taken minimum ~ 1 hour after vaccination.
Body Temperature	X	X	X	X	X	X	X	X	X	X	X	X	X	Section 8.3.2.2 (temperature) and Section 8.3.5 (VRC) Days 1 to 14 will be done by participant and recorded on the VRC. All other measurements will be done by clinic staff.
12-lead ECG	X	X												Section 8.3.3 Day 1 Predose ECG will be done within 24 hours of dosing.
Distribute Paper Vaccination Report Card (VRC)			X											Section 8.3.5 (VRC) Paper VRC will be provided on Day 1.

1-dose Panels C-E and G-H														
	Screening	Study Day											Post-Study	Notes
Scheduled Hour, Day, Week, etc.	Screening -28 to -1 ^b	Day 1 Pre-dose	1	2 ^a	8±1	15±1	29±3	57±3	85±3	115±7	211±14	365±14		Section 8.11.5 Details on variance in procedure collection times
Participant Record Paper VRC			X	X	X	X								Section 8.3.5 (VRC) On the VRC, the participant records information, including solicited and unsolicited (local and systemic) AEs, temperature, medications, and other complaints.
Review Paper VRC Data with Participant				X	X	X	X							Section 8.3.5
Collect Paper VRC From Participant							X							Section 8.3.5.
Postvaccination Observation Period			X											Section 8.11.2 Panel E: Participants will be observed for ~ 8 hours postdose on Day 1 for the five sentinel participants. All other panels: Participants will be observed for ~ 1 hour postdose on Day 1.
Safety Phone Call Follow-up				X										Section 8.3.6 On non-clinic days the, safety phone calls will follow up on AEs, any associated medications and vaccinations.
AE Review		X	X	X	X	X	X							Sections 8.4 and Appendix 3
SAE/ECI/MAAE review		X	X	X	X	X	X	X	X	X	X	X	X	Sections 8.4 and Appendix 3 Nonserious AEs are to be reported from Days 1 to 28. SAEs/ECIs/MAAE and deaths are to be reported throughout the duration of an individual's study participation.
Laboratory Procedures/Assessments														
Serum β-hCG or urine pregnancy test (WOCBP only)	X	X											X	Appendix 2 Pregnancy test on Day 1 to be performed before vaccination.

1-dose Panels C-E and G-H														
	Screening	Study Day											Post-Study	Notes
Scheduled Hour, Day, Week, etc.	Screening -28 to -1 ^b	Day 1 Pre-dose	1	2 ^a	8±1	15±1	29±3	57±3	85±3	115±7	211±14	365±14		Section 8.11.5 Details on variance in procedure collection times
Serum FSH - (WONCBP only)	X													Appendix 2 Confirmatory for WONCBP who are postmenopausal or oophorectomized.
HIV, hepatitis B and C screen (per site SOP)	X													Appendix 2
UDS/BDS/Alcohol Breath (per site SOP)	X													Any additional UDS/BDS are conducted per site SOP
Coagulation: Prothrombin time/International Normalized Ratio	X													Appendix 2
Hematology	X				X	X	X	X	X				X	Section 8.3.7 and Appendix 2
Urinalysis	X				X	X	X	X	X				X	Section 8.3.7 and Appendix 2
Chemistry	X				X	X	X	X	X				X	Section 8.3.7 and Appendix 2
Screening and SARS-CoV-2 Test														
SARS-CoV-2 PCR	X													Appendix 2
Immunogenicity														
Serum Collection for Neutralizing Antibodies by PNA		X				X	X	X	X	X	X	X	X	Leftover main study serum samples to be stored for FBR
Serum Collection for Total Anti-spike IgG and Total Anti-N IgG Antibodies by ELISA		X				X	X	X	X	X	X	X	X	Leftover main study serum samples to be stored for FBR
Serum collection for Immunological Assessments (Panels C, D, G, and H only)		X			X									Leftover main study serum samples to be stored for FBR
PBMC collection for Immunological Assessments (Panels C, D, G, and H only)		X					X							Leftover main study PBMC samples to be stored for FBR
Biomarkers														
Blood (DNA) for Future Biomedical Research		X												Section 8.9 Collect from enrolled participants only.

1-dose Panels C-E and G-H													
	Screening	Study Day										Post-Study	Notes
Scheduled Hour, Day, Week, etc.	Screening -28 to -1 ^b	Day 1 Pre-dose	1	2 ^a	8±1	15±1	29±3	57±3	85±3	115±7	211±14	365±14	Section 8.11.5 Details on variance in procedure collection times

AE=adverse event; β-hCG=beta human chorionic gonadotropin; BDS=blood drug screen; BP=blood pressure; DNA=deoxyribonucleic acid; ECG=electrocardiogram; ECI=event(s) of clinical interest; ELISA=enzyme-linked immunosorbent assay; FBR=future biomedical research; FSH=follicle stimulating hormone; HIV=human immunodeficiency virus; HR=heart rate; ID=identification; IgG=immunoglobulin G; MAAE= Medically Attended Adverse Event; PBMC=peripheral blood mononuclear cells; PCR=polymerase chain reaction; PNA=Pseudo-virus Neutralization Assay; RR=respiratory rate; SAE=serious adverse event; SARS-CoV-2=Severe Acute Respiratory Syndrome Coronavirus (novel); SOP=standard operating procedure; UDS=Urine Drug Screen; VRC=vaccine report card; WOCBP=women of childbearing potential; WONCP=women of nonchildbearing potential
 
a. Safety calls on Day 2 must occur on the day after Day 1 visit, approximately 18 to 30 hours postdose.
 
b. SARS-CoV-2 serology testing will be performed at the screening visit for participants in sentinel Panels A, B and the 5 sentinel participants in panel E only. SARS-CoV-2 seronegative participants will be enrolled in the sentinel Panels A,B and 5 sentinels participants of panel E. Part 2A (with the exception of the 5 sentinel participants in panel E) and Part 2B of the study are not affected by this modification.
													

1.3.2 SoA for 2-Dose Panels (Day 1, Day 57)

2-dose Day 1, Day 57-Panels A-B and I-J															
	Screening	Study Day												Post-Study	Notes
Scheduled Hour, Day, Week, etc.	Screening -28 to -1 ^b	Day 1 Pre-dose	1	2 ^a	8±1	15±1	29±3	57±3	58 ^a	71±1	85±3	115±7	211±14	422±14	Section 8.11.5 Details on variance in procedure collection times
Administrative Procedures															
Informed Consent	X														Section 8.1.1.1
Informed Consent for Future Biomedical Research	X														Section 8.1.1.2
Demographics	X														
Inclusion/Exclusion Criteria	X	X						X							Section 5.0
Participant ID Card	X														Section 8.1.3
Medical History & Vaccination History	X														Section 8.1.4
Prior/Concomitant Medication Review	X	X	X	X	X	X	X	X	X	X	X	X	X	X	Sections 6.6, 8.1.5 Including Non-study Vaccination Review
Assignment of Screening Numbers	X														Section 8.1.6
Assignment of Randomization Number		X													Sections 5.5 and 8.1.7
COVID-19 Symptoms Training		X			X	X	X		X	X	X	X			Section 8.3.7
V591/Placebo Administration			X					X							Section 8.1.8
Clinical Procedures/ Safety Assessment															
Full physical examination	X	X											X	X	Section 8.3.1.1

2-dose Day 1, Day 57-Panels A-B and I-J															
	Screening	Study Day												Post-Study	Notes
Scheduled Hour, Day, Week, etc.	Screening -28 to -1 ^b	Day 1 Pre-dose	1	2 ^a	8±1	15±1	29±3	57±3	58 ^a	71±1	85±3	115±7	211±14	422±14	
Symptoms driven physical exam			X		X	X	X	X		X	X	X			Section 8.3.1.2 Only to be conducted if participant symptoms warrant an exam or at investigator's discretion
Targeted physical examination of injection site			X		X	X		X		X					Section 8.3.1.3 Panels A and B: ~ 8 hours after vaccination on Day 1 and Day 57. Panels I and J: ~ 1 hour after vaccination on Day 1 and Day 57.
Height	X														Section 8.3.1.4
Weight	X							X						X	Section 8.3.1.4
Semi-recumbent Vital Signs (Blood Pressure [BP] and Heart Rate [HR] and Respiratory Rate [RR])	X	X	X		X	X	X	X		X	X	X	X	X	Section 8.3.2 Day 1 predose: within ~ 3 hours of dosing. Panels A and B Postdose: ~ 8 hours after vaccination on Day 1 and Day 57. Panels I and J Postdose: ~ 1 hour after vaccination on Day 1 and Day 57.
Body Temperature	X	X	X	X	X	X	X	X	X	X	X	X	X	X	Section 8.3.2.2 (temperature) and Section 8.3.5 (VRC) Days 1 to 14 and Days 57 to 70 will be done by participant and recorded on the VRC. All other measurements will be done by clinic staff.
12-lead ECG	X	X													Section 8.3.3 Day 1 predose ECG will be done within 24 hours of dosing.

2-dose Day 1, Day 57-Panels A-B and I-J															
	Screening	Study Day												Post-Study	Notes
Scheduled Hour, Day, Week, etc.	Screening -28 to -1 ^b	Day 1 Pre-dose	1	2 ^a	8±1	15±1	29±3	57±3	58 ^a	71±1	85±3	115±7	211±14	422±14	
Distribute Paper Vaccination Report Card (VRC)			X					X							
Participant Record VRC			X	X	X	X		X	X	X					Section 8.3.5 (VRC) Paper VRC will be provided on Day 1 and Day 57. On the VRC, the participant records information, including solicited and unsolicited (local and systemic) AEs, temperature, medications, and other complaints.
Review Paper VRC Data with Participant				X	X	X	X		X	X	X				Section 8.3.5
Collect Paper VRC From Participant							X				X				Section 8.3.5.
Postvaccination Observation Period			X					X							Section 8.11.2 Panels A and B: ~ 8 hours after vaccination on Day 1 and Day 57. Panels I and J: ~ 1 hour after vaccination on Day 1 and Day 57.
Safety Phone Call Follow-up				X					X						Section 8.3.6 On non-clinic days the, safety phone calls will follow up on AEs, any associated medications and vaccinations.
AE Review		X	X	X	X	X	X	X	X	X	X				Sections 8.4 and Appendix 3

2-dose Day 1, Day 57-Panels A-B and I-J																
	Screening	Study Day													Post-Study	Notes
Scheduled Hour, Day, Week, etc.	Screening -28 to -1 ^b	Day 1 Pre-dose	1	2 ^a	8±1	15±1	29±3	57±3	58 ^a	71±1	85±3	115±7	211±14	422±14		
SAE/ECI/MAAE/ review		X	X	X	X	X	X	X	X	X	X	X	X	X	X	Section 8.11.5 Details on variance in procedure collection times
Sections 8.4 and Appendix 3 Nonserious AEs are to be reported from Days 1 to 28 and Days 57 to 84. SAEs/ECIs/MAAEs and deaths are to be reported throughout the duration of an individual's study participation.																
Laboratory Procedures/Assessments																
Serum β-hCG or urine pregnancy test (WONCBP only)	X	X						X							X	Appendix 2 Pregnancy test on Day 1 and Day 57 to be performed before vaccination.
Serum FSH - (WONCBP only)	X															Appendix 2 Confirmatory for WONCBP who are postmenopausal or oophorectomized.
HIV, hepatitis B and C screen (per site SOP)	X															Appendix 2
UDS/BDS/Alcohol Breath (per site SOP)	X															Any additional UDS/BDS are conducted per site SOP
Coagulation: Prothrombin time/International Normalized Ratio	X															Appendix 2
Hematology	X				X	X	X	X		X	X				X	Section 8.3.7 and Appendix 2
Urinalysis	X				X	X	X	X		X	X				X	Section 8.3.7 and Appendix 2
Chemistry	X				X	X	X	X		X	X				X	Section 8.3.7 and Appendix 2
Screening and SARS-CoV-2 Test																
SARS-CoV-2 PCR	X															Appendix 2
Immunogenicity																
Serum Collection for Neutralizing Antibodies by PNA		X				X	X	X		X	X	X	X	X	X	Leftover main study serum samples to be stored for FBR

2-dose Day 1, Day 57-Panels A-B and I-J															
	Screening	Study Day												Post-Study	Notes
Scheduled Hour, Day, Week, etc.	Screening -28 to -1 ^b	Day 1 Pre-dose	1	2 ^a	8±1	15±1	29±3	57±3	58 ^a	71±1	85±3	115±7	211±14	422±14	
Serum Collection for Total Anti-spike IgG and Total Anti-N IgG Antibodies by ELISA		X				X	X	X		X	X	X	X	X	Leftover main study serum samples to be stored for FBR
PBMC collection for Immunological Assessments		X									X				Leftover main study PBMC samples to be stored for FBR
Biomarkers															
Blood (DNA) for Future Biomedical Research		X													Section 8.9 Collect from enrolled participants only.

AE=adverse event; β-hCG=beta human chorionic gonadotropin; BDS=blood drug screen; BP=blood pressure; DNA=deoxyribonucleic acid; ECG=electrocardiogram; ECI=event(s) of clinical interest; ELISA=enzyme-linked immunosorbent assay; FBR=future biomedical research; FSH=follicle stimulating hormone; HIV=human immunodeficiency virus; HR=heart rate; ID=identification; IgG=immunoglobulin G; MAAE= Medically Attended Adverse Event; PBMC=peripheral blood mononuclear cells; PCR=polymerase chain reaction; PNA=Pseudo-virus Neutralization Assay; RR=respiratory rate; SAE=serious adverse event; SARS-CoV-2=Severe Acute Respiratory Syndrome Coronavirus (novel); SOP=standard operating procedure; UDS=Urine Drug Screen; VRC=vaccine report card; WOCBP=women of childbearing potential; WONCBP=women of nonchildbearing potential
 
a. Safety calls on Days 2 and 58 must occur on the day after the Day 1 and Day 57 visits, respectively, approximately 18 to 30 hours postdose.
 
b. SARS-CoV-2 serology testing will be performed at the screening visit for participants in sentinel Panels A, B and the 5 sentinel participants in panel E Only. SARS-CoV-2 seronegative participants will be enrolled in the sentinel Panels A,B and 5 sentinels participants of panel E. Part 2A (with the exception of the 5 sentinel participants in panel E) and Part 2B of the study are not affected by this modification.
															

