Participant Record VRC			X	X	X	X			X	X					Section 8.3.5 (VRC) Paper VRC will be provided on Day 1 and Day 169. On the VRC, the participant records information, including solicited and unsolicited (local and systemic) AEs, temperature, medications, and other complaints.
Review Paper VRC Data with Participant				X	X	X	X		X	X	X				Section 8.3.5
Collect Paper VRC From Participant							X				X				Section 8.3.5.

2-dose Day 1, Day 169-Panels F and K-L														
	Screening	Study Day											Post-Study	Notes
Scheduled Hour, Day, Week, etc.	Screening -28 to -1	Day 1 Pre-dose	1	2 ^a	8±1	15±1	29±3	85±3	169±3	170 ^a	197±3	365±7	534±14	
Postvaccination Observation Period			X						X					Section 8.11.2 Participants will be observed for minimum ~ 1 hour postdose on Day 1 and Day 169.
Safety Phone Call Follow-up				X						X				Section 8.3.6 On non-clinic days the, safety phone calls will follow-up on AEs, any associated medications and vaccinations.
AE Review		X	X	X	X	X	X		X	X	X			Sections 8.4 and Appendix 3
SAE/ECI/MAAE review		X	X	X	X	X	X	X	X	X	X	X	X	Sections 8.4 and Appendix 3 Nonserious AEs are to be reported from Days 1 to 28 and Days 169 to 196. SAEs/ECIs/MAAEs and deaths are to be reported throughout the duration of an individual's study participation.
Laboratory Procedures/Assessments														
Serum β-hCG or urine pregnancy test (WONCBP only)	X	X							X				X	Appendix 2 Pregnancy test on Day 1 and Day 169 to be performed before vaccination.
Serum FSH - (WOCBP only)	X													Appendix 2 Confirmatory for WONCBP who are postmenopausal or oophorectomized.
HIV, hepatitis B and C screen (per site SOP)	X													Appendix 2
UDS/BDS/Alcohol Breath (per site SOP)	X													Any additional UDS/BDS are conducted per site SOP
Coagulation: Prothrombin time/International Normalized Ratio	X													Appendix 2
Hematology	X				X	X	X		X		X	X	X	Section 8.3.7 and Appendix 2

2-dose Day 1, Day 169-Panels F and K-L														
	Screening	Study Day											Post-Study	Notes
Scheduled Hour, Day, Week, etc.	Screening -28 to -1	Day 1 Pre-dose	1	2 ^a	8±1	15±1	29±3	85±3	169±3	170 ^a	197±3	365±7	534±14	Section 8.11.5 Details on variance in procedure collection times
Urinalysis	X				X	X	X		X		X	X	X	Section 8.3.7 and Appendix 2
Chemistry	X				X	X	X		X		X	X	X	Section 8.3.7 and Appendix 2
Screening and SARS-CoV-2 Test														
SARS-CoV-2 PCR	X													Appendix 2
Immunogenicity														

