10.2 Appendix 2: Clinical Laboratory Tests

The tests detailed in Table 14 will be performed by the local laboratory.

Protocol-specific requirements for inclusion or exclusion of participants are detailed in Section 5.1 and 5.2 of the protocol.

Additional tests may be performed at any time during the study as determined necessary by the investigator or required by local regulations.

Table 14 Protocol-required Safety Laboratory Assessments

Laboratory Assessments	Parameters			
Hematology	Platelet Count	RBC Indices: MCV MCH MCHC Reticulocytes	WBC count with Differential: Neutrophils Lymphocytes Monocytes Eosinophils Basophils	
	RBC Count			
	Hemoglobin			
	Hematocrit			
	HbA1c (required at screening only)			
Coagulation	Prothrombin time/International Normalized Ratio (PT/INR)			
Chemistry	BUN	Potassium	AST/SGOT	Total bilirubin (and direct bilirubin, if total bilirubin is elevated above the ULN)
	Albumin	LDH	GGT	
	Creatinine	Sodium	ALT/SGPT	Total Protein
		CPK	Alkaline phosphatase	
Routine Urinalysis	Specific gravity pH, glucose, protein, blood, ketones, bilirubin, urobilinogen, nitrite, leukocyte by dipstick Microscopic examination (if blood or protein is abnormal)			
Pregnancy Testing	Highly sensitive serum or urine hCG pregnancy test (as needed for WOCBP) Additional serum or urine pregnancy tests may be performed, as determined necessary by the investigator or required by local regulation, to establish the absence of pregnancy at any time during the subject's participation in the study.			
Other Screening Tests	FSH (as needed in WONCBP only) Alcohol breath test and drug screen (to include at minimum: cocaine and opiates), sample to be determined by site SOP Serology (HIV antibody, HBsAg, and hepatitis C virus antibody) SARS-CoV-2 serology testing: at the screening visit for participants in sentinel Panels A, B and the 5 sentinel participants in panel E Only. COVID-19 PCR test Additional tests may be done per site SOP with Sponsor agreement.			

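### The pregnancy-test rows in both two-dose schedules name women who cannot become pregnant, and no other text times a pregnancy test before the second dose

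*Combined protocol and SAP*

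**What the plan says.** Section 1.3.2 covers Panels A, B, I and J, which are dosed on Days 1 and 57. Its hCG row is restricted by the words "urine pregnancy test (WONCBP only" and is marked at screening, before dosing on Day 1, on Day 57 and at the post-study visit. The note beside it reads "Pregnancy test on Day 1 and Day 57 to be performed before vaccination" and refers to Appendix 2. The footer defines the label: "WONCBP=women of nonchildbearing potential".

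Section 1.3.3 covers Panels F, K and L, which are dosed on Days 1 and 169. Its hCG row carries the same restriction, with the note "Pregnancy test on Day 1 and Day 169 to be performed before vaccination". Its FSH row is headed "Serum FSH - (WOCBP only", although the note in that row says "Confirmatory for WONCBP who are postmenopausal or oophorectomized".

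Section 1.3.1, for the one-dose panels, limits the hCG row the other way: "urine pregnancy test (WOCBP only". Table 14 in Appendix 2 agrees: "Highly sensitive serum or urine hCG pregnancy test (as needed for WOCBP".

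**The concern.** A pregnancy test limited to women of nonchildbearing potential has no purpose, and it excludes the women the test is meant to protect. V591 is a live recombinant viral vaccine. The protocol excludes pregnant women at entry and requires contraception for at least six months after the last dose.

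A wrong label would matter little if another section repeated the instruction correctly. Section 8 treats adherence to the schedule as mandatory, and Section 8.1.8.1 allows the second dose once the schedule's pre-dose procedures are done. The question is therefore whether any other text would put the test in place before dose 2 if a site followed the row as written.

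**Working it through.** There is no figure in the plan to reproduce. The check compares texts and then counts the people covered.

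**Step 1: the six labels.**

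| Schedule | hCG row | FSH row |
|---|---|---|
| 1.3.1 (one dose) | WOCBP: right | WONCBP: right |
| 1.3.2 (Days 1, 57) | WONCBP: wrong | WONCBP: right |
| 1.3.3 (Days 1, 169) | WONCBP: wrong | WOCBP: wrong |

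Three of six are wrong. The standard is Table 14, which gives hCG to WOCBP and FSH to WONCBP. For FSH in 1.3.3, the row's own note also contradicts its label. The errors stand in current protocol text, not in the amendment log.

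**Step 2: other text that could time a pregnancy test before dose 2.**

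- Section 5.1, inclusion 8, requires a negative test in WOCBP before the first dose only. For testing during and after the intervention it sends the reader to Section 8.4.5.
- Section 8.4.5 covers reporting and follow-up of pregnancies that come to light. It schedules no test, so the cross-reference leads nowhere.
- Section 7.1 stops dosing after a confirmed positive serum test and has eligibility reviewed again before dose 2. It acts on pregnancy status but orders no test.
- Sections 8.1.8.1 and 8.11.2 refer dose-2 procedures back to the schedule.
- Table 14 gives the right population but says only that the test is done as needed, with extra tests at the investigator's judgement or as local rules require. It has no dose-2 timing.
- Appendix 8 counts two serum hCG draws, at screening and post-study. A urine test could be used at dose 2, so this neither schedules nor rules out a test.

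Outside the mislabelled rows and their notes, nothing times a pregnancy test on Day 57 or Day 169. Other procedures, such as the safety laboratory tests, are marked on those days and are not affected.

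**Step 3: who is covered** (Tables 3 and 4).

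- Aged 18 to 55 in two-dose panels: A 5 + B 5 + F 25 = 35, of whom 4 + 4 + 20 = 28 are allocated to V591 and 1 + 1 + 5 = 7 to placebo.
- Over 55 in two-dose panels: I, J, K and L, 4 × 25 = 100.
- All two-dose participants: 35 + 100 = 135.
- Shares: 35/260 = 13.5% of planned enrolment; 35/135 = 25.9% of the two-dose panels.

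These counts include both sexes. The plan does not give the number of women, so the number of WOCBP among the 35 lies between 0 and 35. Few are assumed in the panels of people over 55.

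**The case against.** The strongest reply is that no investigator would take the label at face value. The note in the same row calls for a test before vaccination without limiting the population, and it points to Appendix 2, where the population is correct. At Day 1 the literal label would also contradict inclusion 8.

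Pregnancy is guarded against in other ways too. It is listed under exclusion 10. The eligibility row is itself marked on Day 57 and Day 169. Section 7.1 withholds dose 2 from anyone who no longer qualifies, and investigators may add tests at any time.

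Amendment 04 ends the study, so there may be no second doses left to give. The final visit involves no vaccination and may be replaced by a telephone contact. Finally, the FSH row is marked at screening only and has no part in dose 2, so the dose-2 issue rests on two hCG rows, and the 35 is a ceiling.

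Most of this stands, and it limits the severity. It does not remove the error. None of the safeguards schedules a test: a review of whether a woman is pregnant does not establish it by hCG, and inclusion 8 ties its own test to the first dose. Amendment 04 does not expressly say that second doses have stopped. Section 8.11.4 still sends sites to these same tables for the final visit, at least 56 days after the last vaccination. That visit can fall within the six-month contraception period, and the hCG rows carry a post-study mark.

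**Conclusion.** The concern holds: three population labels are wrong as written. Two of them sit on the only rows that time a pregnancy test before the second dose. The intended population can be recovered from Section 1.3.1, Table 14 and inclusion 8, and an actual omission is unlikely. Sites should still not have to infer the population of a safety test from a label that states the opposite.

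Exposure is at most the WOCBP among 35 planned participants. This assumes few WOCBP over 55 and enrolment as planned. The number of second doses remaining after Amendment 04 is not stated and may be zero. The matter concerns participant safety and the clarity of the protocol. It changes no endpoint, estimate or analysis. It should be corrected, but it is not a critical flaw.

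**What to change.** - Change the hCG row labels in Sections 1.3.2 and 1.3.3 to WOCBP only.
- Change the FSH row label in Section 1.3.3 to WONCBP only.
- In inclusion 8, replace the reference to Section 8.4.5 with a reference to the Schedule of Activities for testing during and after the intervention.
- Tell sites by letter before any remaining second doses or final visits.

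The cost is three labels, one cross-reference and a letter. No procedure, sample or visit is added.
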